2. OBJECTIVES AND ENDPOINTS

The main study will evaluate the effectiveness and safety of ocrelizumab in patients who are in early stage of RRMS.

Specific objectives and corresponding endpoints for the study are outlined below.

Objectives	Corresponding Endpoints
Primary Objective:	
 To evaluate the effectiveness of ocrelizumab in early stage of RRMS 	 Evaluate clinical measures related to disease progression over 4 years in patients in the early stage of their RRMS disease
Overview of the effectiveness measures:	
 Different effectiveness measures 	Related to disability progression:
evaluated for ocrelizumab in early stage of RRMS	 Time to onset of CDP sustained for at least 24 weeks and 48 weeks

Table 1 Objectives and Corresponding Endpoints

Objectives	Corresponding Endpoints
	 Proportion of patients who have confirmed disability improvement (CDI), CDP for at least 24 weeks and 48 weeks at year 1, 2 and 4
	 Proportion of patients who have improved, stable or worsened disability compared with baseline measured by EDSS annually
	 Mean change from baseline in EDSS score over the course of the study
	Other clinical measures and composite endpoints:
	 Time to first protocol-defined event of disease activity
	Time to first relapse
	 Annualized relapse rate
	 Proportion of patient relapse free by week 48, 96, 144 and 192
	 Proportion of patients with no evidence of protocol- defined disease activity (NEDA) over week 96, week 144 and week 192 where disease activity is defined as at least one the following events: protocol-defined relapse; CDP based on increases in EDSS; a T1 Gd- enhanced lesion after Week 8; or a new and/or enlarging T2 hyperintense lesion on MRI after Week 8 compared to the Week 8 MRI scan.
	 Proportion of patients with no evidence of progression (NEP) defined as no progression sustained for at least 24 weeks on all of the following three components (CDP; 20% increase in timed 25 Foot Walk Test [T25FWT]; 20% increase in timed 9 hole peg test [9HPT]) between baseline and week 96/192
	 Proportion of patients with no evidence of progression sustained for at least 24 weeks and no active disease (NEPAD) defined as no progression on all of the three components of NEP (CDP, T25FWT, 9HPT), no new relapse and no enlarging or new T2 or T1 Gd- enhancing lesion between baseline and week 96/192

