T and B cells impact sub-study in France 288 weeks longitudinal, multi- center, sub-study (n=~50) Participating centers are restricted to French investigator centers with PBMC (peripheral blood mononuclear cell) technical and storage capacity.	 Impact of ocrelizumab-dependent B cell depletion on T cell subsets and functions in naïve RRMS patients, indirect impact of ocrelizumab on B cell repopulation and relationship between immunological biomarkers levels and clinical and/or subclinical change assessed by neurological markers in naïve RRMS patients treated with ocrelizumab
Immune sub-study in Germany and other selected countries (n=~80)	 Frequencies of circulating immune cell subsets (B cells, T cells, NK cells, antigen presenting cells)

Objectives	Corresponding Endpoints
Ocrelizumab shorter infusion substudy (approximately 700 patients: of which approximately 550 additional patients and approximately 150 currently participating in the main study)	 Proportion of patients with IRRs occurring during or within 24 hours following the first infusion after randomization to the shorter infusion substudy

The definition of a protocol-defined event of disease activity is the occurrence of at least one of the following while on treatment with ocrelizumab:

- a protocol-defined relapse as defined in Section 4.5.5
- CDP based on increases in EDSS (see Section 4.5.6)
- a T1 Gd-enhanced lesion after Week 8
- a new and/or enlarging T2 hyperintense lesion on MRI after Week 8 compared to the Week 8 MRI scan

3. STUDY DESIGN

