- Life threatening (Common Terminology Criteria for Adverse Events [CTCAE] Grade 4) infusion-related event that occurred during a previous ocrelizumab infusion
- Current active infection other than a fungal nailbed infection. The re-treatment should be delayed until the active infection is treated and patient fully recovered
- CD4 cell count < 250/µL
- Absolute neutrophil count (ANC) <1.0 × 10³/µL
- Elevated aspartate aminotransferase (AST)/ serum glutamic oxaloacetic transaminase (SGOT) or alanine aminotransferase (ALT) /serum glutamic pyruvic transaminase (SGPT) (>3 × the upper limit of normal [ULN]) in combination with either an elevated total bilirubin (>2 × ULN) or clinical jaundice
- Hepatitis B screening tests prior to ocrelizumab administration
 - If total hepatitis B core antibody (HBcAb) was positive at screening, hepatitis B virus (HBV) deoxyribonucleic acid (DNA) measured by polymerase chain reaction (PCR) must be negative in order for a patient to be dosed with ocrelizumab. For patients with negative hepatitis B surface antigen (HBsAg) and positive total HBcAb, HBV DNA testing (by PCR) must be repeated every 24 weeks and evaluated prior to ocrelizumab administration. If it becomes positive, treatment with ocrelizumab must be discontinued and the patient should enter the safety follow-up.
- Any significant or uncontrolled medical condition or treatment-emergent, clinically significant laboratory abnormality
- Ongoing pregnancy or breastfeeding (In case of unplanned pregnancy, treatment should be interrupted, however the patient will remain in the trial and will have the opportunity to re-start ocrelizumab treatment after birth and breastfeeding are over. The total duration of treatment period will be 192 weeks from the date of first dose of ocrelizumab, irrespective of how long the treatment was interrupted due to pregnancy. During pregnancy and breastfeeding, the patient will continue to come for the regular scheduled visits (whenever possible, adhering to the time of scheduled visits as per protocol) and will perform all assessments except MRI.

At the end of the study treatment the patients will be encouraged to be included in a separate LTE (MN39158) study, as applicable, to further evaluate the effectiveness and safety of *ocrelizumab treatment*. This LTE will also aim to evaluate the long-term outcomes with ocrelizumab treatment over the extended period of time in patients with MS.

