4.7 TREATMENT, PATIENT, STUDY, AND SITE DISCONTINUATION

4.7.1 Study Treatment Discontinuation

Patients must discontinue study treatment if they experience any of the following:

- Pregnancy: patients becoming pregnant by chance during the study will be withheld from ocrelizumab treatment, but will remain in trial and will have the opportunity to re-start ocrelizumab treatment after the pregnancy/breastfeeding are over. During pregnancy and breastfeeding, these patients will continue to come for the regular scheduled visits (whenever possible, adhering to the time of scheduled visits as per protocol) and will perform all assessments except MRI. The total duration of treatment period will be 192 weeks from the date of first dose of ocrelizumab, irrespective of how long the treatment was interrupted due to pregnancy.
- Patients who plan to become pregnant during the study will be withheld from ocrelizumab treatment and will follow the recommendations for contraception period after the last infusion with ocrelizumab for at least 6 months or longer in accordance with locally applicable ocrelizumab package leaflet. Upon discontinuation of study treatment, these patients will enter the safety follow-up period but will not restart the study treatment.
- Life-threatening (NCI CTCAE Grade 4) IRR or serious hypersensitivity reaction
- New onset or reactivation of hepatitis B infection
- PML
- Any other serious adverse event, including laboratory values abnormalities, that present an unfavorable benefit-risk of treatment with ocrelizumab as deemed by the investigator.

The primary reason for study treatment discontinuation should be documented on the appropriate eCRF. Patient discontinuing the study treatment prematurely will be further monitored in a safety follow-up (see Section 3.1.4).

Patients who discontinue study treatment prematurely will not be replaced.

Refer to the schedule of activities (see Appendix 1) for details on follow-up assessments to be performed for patients who permanently discontinue study treatment.

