6.4 EFFECTIVENESS ANALYSES

6.4.1 Effectiveness Endpoints

Effectiveness of ocrelizumab will be evaluated by means of a set of endpoints addressing different facets of MS. There is no primary endpoint defined in the main study. These effectiveness endpoints include time to onset of confirmed CDP sustained for at least 24 and 48 weeks, change from baseline in EDSS score over time, relapse rates, MRI-based measures of disease activity and progression or degeneration, measures of cognition and PROs.

For a full list of effectiveness endpoints refer to Section 2.

After the Week 192 visit of the last enrolled patient, approximately 24 weeks and 48 weeks may be needed to allow the confirmation of the last event of the 24-week and 48 week-CDP (CDP/CDI confirmation visit). The main study analysis will be performed after the last CDP and CDI confirmation visit. With respect to CDP confirmation visits, only EDSS data at all the visits occurring in the treatment period of the study and LTE study (for patients who roll over to study MN39158) will be used. Appropriate statistical methods to account for missing confirmation visits will be defined in the SAP.

The evaluation of the clinical effectiveness of ocrelizumab will be based upon the events and assessments in-between baseline and week 192.

For patients who do not have an event by week 192, the time-to-event endpoints will be censored at the time of last visit in the study. A descriptive analysis based on the Kaplan-Meier method will be performed for the time to CDP and other time-to-event endpoints, such as the time to first relapse or the time to first event of disease activity. Cox proportional hazards regression will be used to identify predictors for CDP and other time-to-event endpoints. Variables to be included in the regression model will be region, gender, baseline EDSS, and some other variables, as appropriate. Further details will be specified in the SAP.

The change from baseline in EDSS, as well as other continuous variables, will be primarily analyzed using descriptive statistics, the mean, corresponding 95% CI, standard deviation and other statistics will be presented. Furthermore, the change of EDSS from baseline to each visit will be analyzed by linear mixed models for repeated measures (MMRM) adjusting for covariates such as the respective baseline score, geographical region, and baseline EDSS.

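### Time to first disease activity counts events only on ocrelizumab but follows patients to their last study visit, and the on-treatment limit contradicts the NEDA definition

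*Protocol*

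**What the plan says.** Protocol Section 2 closes with a definition of a protocol-defined event of disease activity: at least one "of the following while on treatment with ocrelizumab", followed by relapse, CDP, a T1 Gd-enhanced lesion after Week 8, or a new or enlarging T2 lesion relative to Week 8.

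The NEDA row of Table 1, repeated in the synopsis, has its own definition, "where disease activity is defined as at least one the following events: protocol-defined relapse; CDP based on increases in EDSS", plus the same two MRI components. It sets no on-treatment limit.

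Section 6.4.1 bases clinical effectiveness on all that happens "based upon the events and assessments in-between baseline and week 192". It censors time-to-event endpoints for event-free patients at their final visit in the study, not at the end of treatment.

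Two groups have follow-up off drug:

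- **Unplanned pregnancy (Sections 3.1.3 and 4.7.1).** Ocrelizumab is withheld, but "the patient will remain in the trial and will have the opportunity to re-start ocrelizumab treatment after birth and breastfeeding are over". She "will perform all assessments except MRI". The clock does not stop: her 192 weeks are counted from the first infusion, "irrespective of how long the treatment was interrupted due to pregnancy".
- **Early discontinuation (Section 3.1.4 and Appendix 2).** Relapses and EDSS are collected 24 and 48 weeks after the last infusion.

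Section 6.8 sets NEDA to no for certain patients who do not complete the study. Section 6.7 mentions women interrupting for pregnancy only as a possible subgroup.

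**The concern.** A time-to-event analysis needs events and time at risk to follow the same rule. Here events are limited to time on drug, while follow-up runs to the last visit. In the Kaplan-Meier estimate, a patient off drug stays in the risk set when nothing that happens to her can count. The hazard over that stretch is understated and the event-free curve sits too high. The error can only favour the drug.

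For NEDA the problem is a contradiction. The endpoint's name uses the protocol-defined disease activity term, which the text under Table 1 restricts, but its own row spells out an unrestricted list. Two programmers could each follow the protocol and classify the same patient differently.

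**Working it through.** The plan gives no figure for this point, so the check is mainly a comparison of texts.

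**Step 1: which definition governs each endpoint**

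| Endpoint | Own definition in Table 1? | On-treatment limit | Follow-up |
|---|---|---|---|
| Time to first protocol-defined event of disease activity | No; relies on the text under Table 1 | Yes | To last study visit (6.4.1) |
| NEDA | Yes, unrestricted, but uses the restricted term in its name | Contradictory | To Weeks 96, 144, 192 |
| NEPAD | Yes; relapse, progression and lesions from baseline to Week 96/192 | No | To Weeks 96, 192 |

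**Step 2: follow one patient.** A woman interrupts for an unplanned pregnancy, has a relapse while off drug that recovers, restarts, reaches Week 192 and has no other activity.

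- Time to first event, as worded: the relapse is not an event, and she is censored event-free at her last visit.
- NEDA by the Table 1 row with 6.4.1: no.
- NEDA by the text under Table 1: yes.
- Section 6.8 does not settle it, because she completed the study.

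**Step 3: what can still be captured**

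- T2 lesions are judged against Week 8, so one formed off drug that persists can appear on the next scan after restart.
- Progression is measured from baseline EDSS (Section 4.5.6), so worsening that begins off drug and is sustained can meet the threshold and be confirmed later.
- What is lost is mainly relapses that recover and transient enhancement. During pregnancy the enhancement is missed because no scan is taken, and no change of definition recovers it.

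**Step 4: size.** If k patients have their only activity off drug, the two NEDA definitions differ by k/1,225. With k = 1 that is 1/1,225 = 0.08 percentage points.

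The documents give no value for k. For illustration only, assume 1% to 8% of patients interrupt for pregnancy and 10% to 40% of those have activity only off drug:

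- Low: 1,225 × 0.01 × 0.10 = 1.2 patients; shift 0.01 × 0.10 = 0.1 points.
- High: 1,225 × 0.08 × 0.40 = 39.2 patients; shift 0.08 × 0.40 = 3.2 points.

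For scale, the 95% half-width of a proportion p is 1.96 × √(p(1−p)/1,225), which is 2.2 points at p = 0.8 and 2.8 points at p = 0.5. Both input ranges are assumptions, so the 0.1 to 3.2 points is not an estimate.

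**The case against.** The best defence is that on treatment simply means within the 192-week treatment period. That period runs on regardless of a pregnancy interruption, and Section 4.5.5 has relapses recorded throughout it. The phrase would then only exclude safety follow-up. This reading is possible, but it is not what the text says. The limit is treatment with ocrelizumab, and Section 4.7.1 lists pregnancy among the reasons for discontinuing study treatment and describes the drug as withheld. The term is not defined anywhere. Even on this reading, patients who stop early keep follow-up time that counts while their events do not.

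Four other objections carry weight:

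- NEDA has a complete unrestricted definition. A reader might infer that a patient who relapses off drug will be scored as NEDA. The documents do not support that, because under the Table 1 row she is not NEDA. Her status is undetermined.
- A reader might extend the point to NEPAD. Its definition never uses the restricted term, so it is outside the problem.
- Not every patient with off-drug activity is misclassified. Anyone with on-treatment activity is already a NEDA failure.
- The numbers may be small. Contraception is required and intending pregnancy is an exclusion. Patients who later plan a pregnancy stop treatment and enter follow-up, so they are not in the interruption group.

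Finally, the protocol defers detail to the main-study SAP, which is not among the documents and may resolve this. The supplied SAP covers only the shorter infusion substudy and plans no efficacy analysis (SAP 4.4).

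**Conclusion.** The concern holds in a limited form. As worded, time to first protocol-defined event of disease activity pairs on-treatment events with follow-up to the last visit, so off-drug time is credited as event-free and the endpoint is biased favourably. For NEDA, the protocol gives two definitions that can classify the same off-drug relapse in opposite ways. It does not establish that such a patient counts as a success.

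The loss is mainly relapses that recover and transient enhancement. The size cannot be derived from the documents: each patient whose sole activity is off drug moves NEDA by about 0.08 points, and how many there are is unknown. The conclusion assumes that withheld means not on treatment, which is the natural reading but not a stated one. The study is descriptive with no primary endpoint, so this is a correction to listed effectiveness endpoints and does not threaten the study as a whole.

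**What to change.** Delete the on-treatment phrase from the definition under Table 1, so that time to first event and NEDA count all events from baseline to Week 192, as Section 6.4.1 already says. State explicitly that off-drug visits before Week 192 are included, both during pregnancy interruptions and in follow-up after early discontinuation. Say how this fits with the 6.4.1 rule limiting which EDSS visits can confirm CDP.

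If an on-treatment version is wanted, report it as a sensitivity analysis. Define on treatment (for example, a stated interval after the last infusion) and censor follow-up at that same point, so that events and time at risk match.

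The cost is one phrase in the protocol, a matching line in the main-study SAP and some programming. No new data are needed. Reported results may be slightly less favourable.

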3.1 DESCRIPTION OF THE STUDY

The main study is a prospective, multicenter, open-label, single-arm effectiveness and safety study in patients with early stage RRMS. The first dose of ocrelizumab will be administered as an initial dose of two 300-mg infusions (600 mg total) in 250 mL 0.9% sodium chloride each separated by 14 days (i.e., Days 1 and 15) followed by one 600-mg infusion in 500 mL 0.9% sodium chloride every 24 weeks (± 14 days) for the remainder of the study duration.

Patients will be assessed for effectiveness and safety every 24 weeks as described in the Schedule of Assessments presented in Appendix 1.

The study will consist of the following periods:

- Screening period: Up to 4 weeks
- Treatment period: Open-label treatment period of 192 weeks (i.e. 24 weeks after the last dose of ocrelizumab, which will be administered at Week 168)
- A *safety* follow-up period of 48 weeks *after the last infusion of the study drug*, as explained below

Safety Follow-up Period: Patients who discontinue treatment early for any reason and patients who complete the study treatment period and do not continue in a separate long-term extension (LTE) study, will be followed up for 48 weeks after the last infusion of study drug. When patients begin an alternative treatment for MS (see section 4.4.1 "Prohibited Therapy"), they will be discontinued from the study.

Patients who discontinue study treatment and switch to commercially marketed ocrelizumab, either after completion of the 192 weeks Treatment Period or after early discontinuation of the 192 weeks Treatment Period, will not enter the safety Follow-up Period.

A structured telephone interview will be conducted by site personnel every 8 weeks between the study visits (starting after the site visit at 8 weeks) during the treatment period to identify and collect information on any changes in the patient's health status that warrant an unscheduled visit (including new or worsening neurological symptoms) and possible events or infections.

3.1.1 Overview of Study Design

Figure 1 presents an overview of the study procedures. A schedule of assessments is provided in Appendix 1.

Figure 1 Overview of Study Procedures

MRI = magnetic resonance imaging; OCR = ocrelizumab; NEDA = no evidence of disease activity

3.1.2 Screening

After providing written informed consent, patients will enter a screening period (up to 4-weeks) to be evaluated for eligibility.

Re-screening of patients is allowed in this protocol.

3.1.3 Treatment Period

Eligible patients will be treated with an initial dose of two 300-mg infusions (600 mg total) in 250 mL 0.9% sodium chloride each separated by 14 days (i.e., Days 1 and 15) followed by one 600-mg infusion in 500 mL 0.9% sodium chloride every 24 weeks (±14 days) for the remainder of study duration.

Ocrelizumab—F. Hoffmann-La Roche Ltd 34/Protocol MA30143, Version 10.0

Additional patients enrolled into the shorter infusion sub-study were randomized into 2 groups at week 24 visit. One group received 600 mg ocrelizumab in 500 mL 0.9% sodium chloride infused over approximately 3.5 hours every 24 weeks (±14 days) for the remainder of the study duration (as in the main study) and the other group received 600 mg ocrelizumab in 500 mL 0.9% sodium chloride infused over 2.0 hours followed by 100 mL 0.9% sodium chloride given as a slow infusion over the remaining 1.5 hours, in order to mimic the standard-length infusion (3.5 hour) starting from week 24 for the remainder of the study duration. Please see Appendix 10 for further details. Patients already enrolled in the main study were offered to participate in the shorter infusion substudy and were randomized into the above 2 groups at the next main study visit if found eligible and after providing written informed consent. The protocol amendment version 8.0 marked the completion of the shorter infusion substudy and patients will continue under the main study protocol.

Based on the results of the primary analysis of the shorter infusion substudy, patients will be allowed to switch from the conventional ocrelizumab infusion (~3.5 hours) to the shorter ocrelizumab infusion (~2.0 hours) at any visit after the Week 24 visit based on the schedules of infusion as per the protocol, after providing written informed consent and in agreement with their treating physician, provided they have not experienced any previous serious IRRs with ocrelizumab treatment. While on the shorter infusion, the patients can switch back to the conventional infusion, in agreement with their treating physician. If patients develop a serious IRR while on the shorter infusion, they will be switched to the conventional infusion and should not be restarted on the shorter infusion at any following infusion visit.

*All l*aboratory samples can be taken up to 2 weeks prior to the scheduled study visit. Local laboratory results for hematology, biochemistry and CD4 should be available prior to dosing as they are re-treatment criteria. Local laboratory results for CD8 and CD19 may be available later, as they do not need to be verified prior to re-treatment. Samples for NfL, anti-drug antibodies (ADA), and ocrelizumab concentration are collected and sent to the central laboratory for analysis. Please see Section 4.5.8 for further details

After the end of treatment period visit of the last enrolled patient, approximately 24 weeks and 48 weeks may be needed to allow the confirmation of the last event of the 24-week and 48-week CDP (CDP/CDI confirmation visit). For those patients presenting with an EDSS change at the end of the treatment period and who roll over to the LTE study (Study MN39158), the 24-week and 48-week CDP confirmation visits will occur during the LTE study (Study MN39158). For patients who discontinue the study (e.g., move onto commercial ocrelizumab, or start treatment with another DMT), the EDSS CDP confirmatory assessments will not be performed.

Sub-studies will be conducted in selected countries according to local approvals and procedures. Please refer to Appendices 8, 9, and 10 for the sub-study protocols.

Criteria for Re-Treatment with Ocrelizumab

Prior to re-treatment with ocrelizumab, patients will be evaluated for the following conditions and laboratory abnormalities. If any of these are present prior to re-dosing, further administration of ocrelizumab should be suspended until these are resolved or withheld indefinitely:

- Life threatening (Common Terminology Criteria for Adverse Events [CTCAE] Grade 4) infusion-related event that occurred during a previous ocrelizumab infusion
- Current active infection other than a fungal nailbed infection. The re-treatment should be delayed until the active infection is treated and patient fully recovered
- CD4 cell count < 250/µL
- Absolute neutrophil count (ANC) <1.0 × 10³/µL
- Elevated aspartate aminotransferase (AST)/ serum glutamic oxaloacetic transaminase (SGOT) or alanine aminotransferase (ALT) /serum glutamic pyruvic transaminase (SGPT) (>3 × the upper limit of normal [ULN]) in combination with either an elevated total bilirubin (>2 × ULN) or clinical jaundice
- Hepatitis B screening tests prior to ocrelizumab administration
 - If total hepatitis B core antibody (HBcAb) was positive at screening, hepatitis B virus (HBV) deoxyribonucleic acid (DNA) measured by polymerase chain reaction (PCR) must be negative in order for a patient to be dosed with ocrelizumab. For patients with negative hepatitis B surface antigen (HBsAg) and positive total HBcAb, HBV DNA testing (by PCR) must be repeated every 24 weeks and evaluated prior to ocrelizumab administration. If it becomes positive, treatment with ocrelizumab must be discontinued and the patient should enter the safety follow-up.
- Any significant or uncontrolled medical condition or treatment-emergent, clinically significant laboratory abnormality
- Ongoing pregnancy or breastfeeding (In case of unplanned pregnancy, treatment should be interrupted, however the patient will remain in the trial and will have the opportunity to re-start ocrelizumab treatment after birth and breastfeeding are over. The total duration of treatment period will be 192 weeks from the date of first dose of ocrelizumab, irrespective of how long the treatment was interrupted due to pregnancy. During pregnancy and breastfeeding, the patient will continue to come for the regular scheduled visits (whenever possible, adhering to the time of scheduled visits as per protocol) and will perform all assessments except MRI.

At the end of the study treatment the patients will be encouraged to be included in a separate LTE (MN39158) study, as applicable, to further evaluate the effectiveness and safety of *ocrelizumab treatment*. This LTE will also aim to evaluate the long-term outcomes with ocrelizumab treatment over the extended period of time in patients with MS.
Figure 2 **Overview of End of Treatment Period** *provides an overview of the end-of-treatment period.* (*Please see Section* 3.1.4).

A structured telephone interview will be conducted by site personnel every 8 weeks between the study visits (starting after the site visit at 8 weeks) during the treatment period to identify and collect information on any changes in the patient's health status that warrant an unscheduled visit (including new or worsening neurological symptoms) and possible events or infections.

LTE = *Long-term extension; MS* = *Multiple sclerosis*

3.1.4 Safety Follow-up Period

Patients who discontinue treatment early for any reason and patients who complete the 192 weeks Treatment Period and do not continue in a separate LTE study will be followed up for 48 weeks after the last infusion of study drug. When patients begin an alternative treatment for MS (see section 4.4.1 "Prohibited Therapy"), they will be discontinued from the study.

Patients who discontinue study treatment and switch to commercially marketed ocrelizumab, either after completion of the 192 weeks Treatment Period or after early discontinuation of the 192 weeks Treatment Period, will not enter the *Safety* Follow-up Period.

A schedule of assessments for the *Safety* Follow-up Period is presented in Appendix 2.

During the *Safety* Follow-up Period, patients will be formally assessed at clinical visits every 24 weeks.

Ocrelizumab—F. Hoffmann-La Roche Ltd 37/Protocol MA30143, Version 10.0 Related SAEs must be collected and reported regardless of the time elapsed from the last study drug administration, even if the study has been closed.

Unrelated SAEs must be collected and reported during the study through the end of the Safety Follow-Up Period, which is 48 weeks after the last infusion. Non-serious adverse events have to be reported until the end of Safety Follow-up Period.

For patients withdrawing from treatment early, every effort should be made to complete the *Safety* Follow-up Period and all related assessments.

